TITLE	A randomized, double-blind, phase IIb study to investigate the efficacy, safety, tolerability and pharmacokinetics of a single dose regimen of ferroquine (FQ) with artefenomel (OZ439) in adults and children with uncomplicated Plasmodium falciparum malaria
INVESTIGATOR/TRIAL LOCATION	Africa and previously in Asia (recruitment in Asia is closed)
STUDY OBJECTIVES	
Primary objective
 
 To determine whether a single dose combination of OZ439/FQ is an efficacious treatment for uncomplicated Plasmodium falciparum (P. falciparum) malaria in adults and children 
Secondary objectives
 
 To evaluate the efficacy of OZ439/FQ: 
 To determine the incidence of recrudescence and re-infection To determine the time to relief of fever and parasite clearance To evaluate the safety and tolerability of OZ439/FQ To evaluate the pharmacokinetics of OZ439/FQ: 
 To characterize the pharmacokinetics of OZ439 in plasma, FQ and its active metabolite SSR97213 in blood To determine the blood/plasma ratio for FQ and SSR97213 in some patients at limited time points in selected sites. To further explore efficacy of OZ439/FQ: 
 To evaluate the proportion of patients with gametocytes at each parasitological assessment To characterize gametocyte carriage To evaluate the relationship between Adequate Clinical & Parasitological Response (ACPR) and exposure to OZ439/FQ To explore the relationship between Kelch-13 genotype and parasite clearance kinetics To explore in vitro drug resistance of P. falciparum infecting patients >14 years old in Vietnamese sites.
STUDY DESIGN	
A randomized, double-blind single-dose treatment, 3 to 4 dose-regimen study in patients with uncomplicated Plasmodium falciparum malaria. Adults and children will be included sequentially in four cohorts through a progressive age step-down procedure and FQ dose step-up procedure (pre-defined data of patients >14 years and body weight ≥ 35 kg exposed to the 3 first lowest doses in parallel will be reviewed before testing 1200 mg FQ dose in association with 800 mg OZ439).
 
At the end of each cohort (or sub-Cohort 1a and 1b), a safety review of adverse events, potentially clinically significant abnormalities (PCSAs) for clinical laboratory test results, vital signs, and 12-lead ECGs will be performed. For patients >14 years (Cohort 1), FQ/active metabolite (SSR97213) blood concentration/QTc effect modelling will be done by a Sponsor's independent unblinded statistician and reviewed by an independent Data Monitoring Committee (DMC). This PK/QTc analyses may or may not be reviewed by the

	
DMC at the same time as the safety data review and therefore may or may not be considered by DMC for DMC decision rule to proceed to the 1200 mg FQ dose in association with 800 mg OZ439 in that age category. The DMC will further determine if the range of 3 or 4 FQ doses in association with 800 mg OZ439 can be assessed in the lower age cohorts.
 
The DMC could also decide to enroll additional patients in a same age cohort for collecting more safety data.
 
In addition, interim fertility analyses on polymerase chain reaction (PCR)-adjusted ACPR at Day 28 will be performed using Bayesian methodology when approximately 50 patients per treatment arm and thereafter every time another 25 patients per treatment arm have completed Day 28 assessment.
 
The decision to step down with age cohorts will be based on safety.


STUDY POPULATION Main selection criteria:
	
Inclusion criteria
 
 • Male or female patient aged >6 months old and <70 years old: 
 - Cohort 1 = 14 years <age <70 years and body weight ≥35 kg, - Cohort 2 = 5 years <age ≤14 years; - Cohort 3 = 2 years <age ≤5 years; - Cohort 4 = 6 months <age ≤2 years. • Body weight ≥5 kg and ≤90 kg. • Presence of mono-infection by P. falciparum with: Fever, as defined by axillary temperature ≥37.5°C or oral/rectal/tympanic temperature ≥38°C, or history of fever in the previous 24 hours (history of fever must be documented) and, microscopically (blood smear) confirmed parasite infection, ranging from 1000 to 100 000 asexual parasites/μL of blood. • Informed Consent Form signed by the patient or parent or legally acceptable representative of the minor patient. 
Main exclusion criteria
 
 • Presence of severe malaria (according to WHO definition). • Anti-malarial treatment: 
 - With piperquine -based compound, mefloquine, naphthoquine or sulphadoxine/pyrimethamine (SP) within the previous 6 weeks (after their inhibition of new infections has fallen below 50%). - With amodiaquine or chloroquine within the previous 4 weeks. - With quinine, halofantrine, lumefantrine-based compounds and any other anti-malarial treatment or antibiotics with antimalarial activity (including cotrimoxazole, tetracyclines, quinolones and fluoroquinolones, and azithromycin) within the past 14 days. - With any herbal products or traditional medicines, within the past 7 days. • Known history or evidence of clinically significant disorders. • Previous treatment within 5 times the half-life or within the last 14 days, whichever the longest which are: P-gp substrates, CYP2D6 main substrates and/or strong CYP2C or CYP3A inhibitors and/or moderate inhibitors but inhibiting both CYP2C and CYP3A and/or CYP inducers. • Mixed Plasmodium infection. • Severe vomiting. • Severe malnutrition.

	
 • Laboratory parameters with clinical significant abnormalities and/or reaching critical values. For Liver Function Test: (LFT) aspartate transferase [AST >2 upper limit of normal (ULN)], or alanine transferase [ALT >2 ULN] or total bilirubin [>1.5 ULN]. • Presence of Hepatitis A IgM (HAV-IgM), Hepatitis B surface antigen (HBs Ag) or Hepatitis C antibody (HCV Ab). • Previous participation in any malaria vaccine study or received malaria vaccine in any other circumstance. • Female patient of child bearing potential or male patient having a partner of child bearing potential not willing to use an effective contraceptive(s) method(s) for the duration of the study. • Positive pregnancy test at study screening for female participants of childbearing potential. • Known history of hypersensitivity, allergic or anaphylactoid reactions to ferroquine or other - aminoquinolines or to OZ439 or OZ277 or to any of the excipients. • Family history of sudden death or of congenital prolongation of the QTc interval or known congenital prolongation of the QTc-interval or any clinical condition known to prolong the QTc interval eg, patients with a history of symptomatic cardiac arrhythmias or with clinically relevant bradycardia. • QTcF >450 ms at screening or pre-dose. • Hypokalemia (<3.5 mmol/L), hypocalcemia (<2.0 mmol/L) or hypomagnesemia (<0.5 mmol/L) at screening or pre-dose. • Any treatment known to induce a lengthening of QT interval.
Total expected number of patients:	Approximately 495 (in case of 3 treatment arms, scenario A) or 662 (in case of 4 treatment arms, scenario B) African patients (approximately 165 per treatment arm), plus 21 Asian patients.
Expected number of sites:	Approximately 18 sites in Africa and Asia
STUDY TREATMENTS	
Investigational Products Formulation	Ferroquine (FQ): Capsules of 5, 30, 100 and 200 mg and matching placebo Artefenomel (OZ439): Individual sachets containing 150, 200, 300, 400, 600 and 800 mg OZ439 + TPGS granules for oral suspension.
Route of administration:	Oral route, fasted conditions (3 hours)
Dose regimen:	
3 to 4 treatment arms for the combination of FQ and OZ439.
 
For patients ≥ 35 kg, 3 to 4 treatment arms of FQ will be assessed along with a fixed dose of OZ439:
 
 - Treatment arm #1: OZ439 800 mg and FQ 400 mg in single dose; - Treatment arm #2: OZ439 800 mg and FQ 600 mg in single dose; - Treatment arm #3: OZ439 800 mg and FQ 900 mg in single dose; - Treatment arm #4: OZ439 800 mg and FQ 1200 mg in single dose will be assessed, if the DMC gives green light to proceed with this dose. 
Patients <35 kg will receive weight-adjusted doses for OZ439 predicted to achieve exposure (based on AUC) not exceeding 1.5-fold that of a 60 kg adult and not exceeding that of the lightest adult (35 kg) for the lightest patient in each weight band.
 
Patients <35 kg will receive weight adjusted doses for FQ, predicted to achieve FQ and SSR97213 exposure (based on mean C_{max} and AUC) not exceeding 1.3-fold that of a lightest adult (35 kg) for the lightest patient in each weight band.


PRIMARY AND SECONDARY ENDPOINTS
	
Primary endpoint: PCR-adjusted Adequate Clinical and Parasitological Response (ACPR) at Day 28
 
Secondary endpoints
 
Efficacy endpoints
 
 • PCR - adjusted ACPR at Day 42 and 63. • PCR - crude ACPR at Day 28, 42 and 63. • Kaplan Meier analysis for: 
 - Time to re-emergence; - Time to recrudescence; - Time to re-infection. • Parasite clearance time (PCT). • Fever clearance time (FCT). • Parasite reduction rate (PRR). 
Safety endpoints
 
 • Adverse events, including Serious Adverse Events (SAE), Adverse Event of Special Interest (AESI) and Treatment Emergent Adverse Event (TEAE). • Clinical laboratory tests, vital signs and ECG, including: 
 - Liver Function test (LFT); - QTc assessment. • Physical examination and clinical signs and symptoms related to uncomplicated P. falciparum malaria (fever, dizziness, headache, nausea, anorexia, vomiting, diarrhea, itching, urticaria, skin rash, abdominal pain, joint pain, muscle pain, palpitations, sleep problems, confusion, hearing problems, vision problems, and fatigue). 
Pharmacokinetic (PK) endpoints
 
 • Pharmacokinetic parameters (mainly CL/F, Vss/F, C_{max}, AUC as relevant) of OZ439 in plasma, FQ and SSR97213 in blood and plasma • Blood/plasma ratio for FQ and SSR97213 (some patients in selected sites). 
Exploratory endpoints
 
 • Time to clearance of gametocytemia on blood smear for patients with gametocytes at baseline. • Time to appearance of gametocytemia on blood smear for patients with no gametocytes at baseline and time to clearance. • RT-PCR to measure gametocyte maturation stage (expression of Pfs25 mRNA) in patients >5 years. • Correlation between Kelch-13 genotype status and parasite clearance kinetics. • Define phenotypic and genotypic resistance pattern to conventional ACT of P. falciparum infecting patients aged >14 years old in Vietnamese sites. • In vitro susceptibility testing of P. falciparum infecting patients aged >14 years old in Vietnamese sites to OZ439, FQ and both drugs.

ASSESSMENT SCHEDULE
	
Refer to study flow chart

STATISTICAL CONSIDERATIONS

Analysis population:

The primary efficacy analysis population will be the Per-Protocol (PP) population defined as “lower” naturally acquired immunity (NAI) population”, children ≤5 years in Africa.

Sample size determination:

This protocol is adaptive allowing futility at pre-specified interim points during the conduct of the study. At each interim time point, tests for futility will be performed. Recruitment will cease to a particular treatment arm if the pre-specified criterion for futility is reached. Interim assessment of futility will occur after recruitment of approximately 50 evaluable patients per treatment arm for the 1st futility analysis and every 25 patients per treatment arm thereafter for the 3 other interim analyses (including 75, 100 and 125 evaluable patients per treatment arm, respectively). Recruitment continues until each treatment arm is deemed to be futile or until 150 evaluable patients per treatment arm for the final analysis is reached.

Given the adaptive nature of the study design, the total number of patients to be recruited can only be estimated. Simulations for different PCR-adjusted ACPR responses at Day 28 showed that a sample size of 150 evaluable patients per treatment arm will provide ≥80% probability to reject the null hypothesis (H0: probability of PCR-adjusted ACPR at Day 28 ≤0.90) at the final analysis, for the true rate ≥96.4%.

In addition, a minimum of 15 African patients older than 5 years per treatment arm (likely to have higher NAI and therefore not included in the efficacy analyses) will be included for the DMC safety review.

Primary analysis:

Within each treatment arm, the following null hypothesis will be tested:

$$H_0: p \leq 0.90$$

Against the one sided alternative:

$$H_1: p > 0.90$$

where p is the probability of PCR-adjusted ACPR at Day 28.

The study will follow a group sequential design with up to 4 interim futility analyses, the first one when approximately 50 evaluable patients per treatment arm have reached Day 28 and thereafter every time another 25 evaluable patients per treatment arm (until the final analysis including 150 evaluable patients) have reached Day 28.

At each interim analysis, one of the following potential decisions is to be made:

- The treatment arm is stopped for futility if the posterior probability of H0 (that is, response rate is below 90%) given the data accumulated at the look for the treatment arm in question is too large, that is, $Pr(H_0|data) \geq 0.30$.
- The treatment arm advances to the next stage if the above conditions is not met (even if the observed response rate is 95% or greater).

A Beta (9.5, 0.5) distribution will be used as prior distribution for the response rate and combined with a binomial likelihood to get a Beta posterior distribution and calculate the posterior probability.

At the final analysis, providing the treatment arm has not been stopped for futility, the null hypothesis will be rejected and efficacy of the treatment arm demonstrated if the lower limit of the exact 95% confidence interval using Clopper-Pearson method is >90%.

	
Analysis of secondary endpoints
 
Secondary efficacy variables will be summarized descriptively with incidence rates or standard descriptive methods, including 95% confidence intervals, as appropriate and using PCSAs criteria for relevant safety parameters. Time to event variables will be summarized with Kaplan-Meier estimates of the survival function.
 
The relationship between QTc and FQ & SSR97213, respectively and OZ439 concentrations will be explored graphically and by mixed effect modeling. Prediction (estimate and 90% CI) at the observed geometric mean of C_{max} will be presented for each treatment arm. Three PK/QTc analyses are planned (one for Cohort 1a and a second based on the pool of Cohort 1a & 1b for DMC review, the last one will take into account all cohorts for the final analysis).
 
Standard descriptive statistics on OZ439, FQ and SSR97213 concentration data and PK parameters, blood/plasma ratio for FQ and SSR97213.
 
Relationship between PCR-adjusted ACPR and dose, concentration or exposure to OZ439/FQ will be explored through logistic regression.
 
Safety:
 
The on-treatment phase will be defined as the start time of investigational medicinal product (IMP) administration up to end of study (EOS). All TEAEs will be summarized (counts and percent) by primary system organ class, preferred term and treatment group.
 
Potentially Clinically Significant Abnormalities (PCSAs) for clinical laboratory test results, vital signs, and 12-lead ECGs (manual readings, mean values of the 3 replicates) will be listed, flagged and summarized for treatment group.
 
In addition, raw data and changes from baseline for some relevant parameters (ECGs, vital signs and laboratory parameters) will be summarized in descriptive statistics and summary plots if relevant.


DURATION OF STUDY (per patient)
	
Screening or predose on Day -1.
 
Treatment with OZ439/FQ single dose on Day 0.
 
Hospitalization at minimum for 48 hours post-dose (African patients greater than 5 years) or 72 hours post -dose (all Asian patients and African patients ≤5 years) or for a maximum of 7 days, depending on age, parasite and fever clearance, clinical judgment and patient convenience.
 
Note: those patients discharged at 48 or 72 hours or later but prior to D7 will need to return to the investigational site for scheduled assessments up to Day 7.
 
In case the patient is discharged after Day 3, patient has to perform the Day 3 discharge examinations.
 
Following discharge, patients will return for further assessment up to Day 63. Total duration will be up to 67 days for each patient.

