11.1 DETERMINATION OF SAMPLE SIZE

This protocol is adaptive allowing futility at pre-specified interim points during the conduct of the study. At each interim time point, tests for futility will be performed. Recruitment will cease to a particular treatment arm if the pre-specified criterion for futility is reached. Interim assessment of futility will occur after recruitment of approximately 50 evaluable patients per treatment arm for the 1st futility analysis and every 25 evaluable patients per treatment arm thereafter for the 3 other interim analyses (including 75, 100 and 125 evaluable patients per treatment arm, respectively). Recruitment continues until each treatment arm is deemed to be futile or until 150 evaluable patients per treatment arm for the final analysis is reached. In case of high recruitment rate (ie, fast recruitment), not all the futility analyses may be performed.

Given the adaptive nature of the study design, the total number of patients to be recruited can only be estimated. Simulations for different PCR-adjusted ACPR responses at Day 28 showed that a sample size of 150 evaluable patients per treatment arm will provide $\geq 80\%$ probability to reject the null hypothesis (H_0 : probability of PCR-adjusted ACPR at Day 28 ≤ 0.90) at the final analysis, for the true rate of 96.4%. Recruitment will therefore continue until each treatment arm is deemed to be futile or until 150 evaluable patients per treatment arm is reached.

In addition, a minimum of 15 African patients older than 5 years per treatment arm (likely to have higher NAI and therefore not included in the efficacy analyses) will be included for the DMC safety review.

Lower numbers of patients per treatment arm may be recruited in the event of a poorly efficacious dose or doses (ie, futility).

Thus the targeted number of African patients recruited to this study will be approximately 495 (in case of 3 treatment arms, scenario A, approximately 165 patients/arm) or approximately 662 (in case of 4 treatment arms, scenario B, approximately 165 patients/arm).

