11.4.3.2 Analyses of secondary efficacy endpoints

See [Section 9.2.1](#) for secondary efficacy endpoints details

- PCR-adjusted ACPR (4-term composite criterion) at Day 42 and Day 63
PCR-adjusted ACPR, Early Treatment Failure (ETF), Late Clinical Failure (LCF) and Late Parasitological Failure (LPF) will be analyzed at Day 42 and Day 63 separately thanks to a frequency table ie, proportion, percentage and exact binomial 95% confidence intervals (two-sided by using Clopper-Pearson method for calculating binomial confidence intervals) by cohort and treatment arm (one table including all patients and one table per cohort).
- PCR-crude ACPR at Days 28, 42 and 63
Same analysis using Clopper-Pearson method will be done on PCR-crude ACPR at Days 28, 42 and 63. The dose-response association of single-dose OZ439/FQ for PCR-crude ACPR will also be evaluated.
- Time to re-emergence, to recrudescence, to re-infection, time to parasite clearance (PCT) and time to fever clearance (FCT).
Time to event variables (like time to re-emergence, time to recrudescence, time to re-infection, [FCT], [PCT]) will be analyzed using Kaplan-Meier estimators. Unless specified otherwise, all survival times will be calculated from the date/hour of first study drug intake to the first time to which the event occurred. For each variable, an overall overview including number of events (frequency and %), 25%, median and 75% quantile with 95% CI (expressed in weeks), cumulative incidence of events with 95% CI will be provided in a summary table for all patients and for each cohort separately. Survival curves will be plotted by representing each treatment arm for all patients and separately for each cohort.
- Parasite reduction ratio (PRR)
The calculations and modeling for the PRR will be further discussed in the SAP. This will be calculated using microscopic and, when available, qPCR determined parasitemia.
- Parasitemia
Descriptive statistics (n, mean, geometric mean, standard deviation, median, Q1, Q3, minimum, and maximum) for parasitemia data (number of parasites/ μ L) (raw data and absolute change from baseline) will be displayed at each post-baseline assessment. Time profile plots (Mean \pm SEM) of parasitemia will be provided for each treatment arm, one curve per arm and also for each cohort separately. These analyses will be done using microscopic and qPCR (in patients >5 years) determined parasitemia.

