11.4.5.3 Analysis of pharmacokinetic/pharmacodynamic data

11.4.5.3.1 Relationship between ACPR and dose or concentrations

For each cohort and for all patients separately, the dose-response association of single-dose OZ439/FQ for PCR-adjusted ACPR will demonstrate how the probability of a response in PCR-adjusted ACPR increases with increasing dose OZ439/FQ thanks to a logistic regression with SAS® PROC LOGISTIC by using ACPR data at Days 28, 42 and 63. Same analysis will be done between PCR-adjusted ACPR and exposure.

Results of logistic regressions of PCR-adjusted ACPR on dose (respectively FQ/SSR97213 blood or OZ439 plasma concentrations) of OZ439/FQ will be provided in a summary table including odds ratio estimates, the corresponding 95% Wald confidence intervals and p-value.

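### If an arm closes early for futility, the all-patient dose-response and recurrence comparisons can be confounded by enrolment period; the plan should compare concurrently randomised patients

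*Protocol*

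**What the plan says.** Synopsis (Sample size determination) and Section 11.1: futility is judged arm by arm. "Recruitment will cease to a particular treatment arm if the pre-specified criterion for futility is reached". The others carry on: "Recruitment continues until each treatment arm is deemed to be futile or until 150 evaluable patients per treatment arm". The first look is at about 50 evaluable patients per arm and the later looks are at further steps ("including 75, 100 and 125 evaluable patients per treatment arm, respectively"). Section 11.1 adds: "In case of high recruitment rate (ie, fast recruitment), not all the futility analyses may be performed".

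Three sets of between-arm analyses are then planned:

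- Section 11.4.5.3.1 fits logistic models per cohort and for all patients, using Days 28, 42 and 63: "Results of logistic regressions of PCR-adjusted ACPR on dose (respectively FQ/SSR97213 blood or OZ439 plasma concentrations) of OZ439/FQ will be provided" with odds ratios, 95% Wald intervals and p-values. The synopsis describes the same work as exploratory: "Relationship between PCR-adjusted ACPR and dose, concentration or exposure to OZ439/FQ will be explored through logistic regression".
- Section 11.4.3.2, on crude response: "The dose-response association of single-dose OZ439/FQ for PCR-crude ACPR will also be evaluated".
- Section 11.4.3.2, on time to re-emergence, recrudescence and re-infection: "Survival curves will be plotted by representing each treatment arm for all patients and separately for each cohort".

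No passage limits these to concurrently randomised patients or mentions enrolment period. Section 8.4 stratifies the third randomisation list by region and age class, not by time.

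**The concern.** Randomisation protects comparisons among patients who could have been allocated to any of the arms compared. After one arm closes, later children cannot be allocated to it. In a table or model that pools all patients by arm, the closed arm then represents the early period only, while the surviving arms mix early and late periods. Anything that changes with time becomes associated with dose.

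The endpoints most exposed are PCR-crude ACPR, re-emergence and re-infection, because they depend on transmission while the child is followed. They also matter for the trial's purpose. Section 4.2.2 wants to demonstrate an FQ dose effect, to document FQ's part in preventing recrudescence and re-infection, and to choose the Phase III dose. In the earlier FQ/artesunate study cited there, the dose effect showed on uncorrected cure (50.0%, 60.0%, 74.2%), not clearly on PCR-adjusted cure (93.3%, 97.1%, 96.8%). A false gradient, or a masked real one, would therefore fall on the outcome most likely to be read for dose choice.

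**Working it through.** **1. The plan's own figure.** Success needs a Clopper-Pearson lower 95% limit above 0.90. At n = 150 the limit is 0.906 for 143 successes and 0.898 for 142, so at least 143 are needed. Exact binomial power at 96.4% is 82.5%, or 81.7% with the four futility looks. This agrees with the protocol's figure of at least 80%.

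**2. How often an arm closes.** With x successes in N, the posterior is Beta(9.5 + x, 0.5 + N − x), and the arm stops if Pr(p ≤ 0.90) ≥ 0.30. At N = 50, 5 failures give 0.367 (stop) and 4 give 0.210 (continue). The stopping boundaries are 5/50, 7/75, 10/100 and 12/125 failures. Exact closure probabilities:

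| True PCR-adjusted rate | at 50 | at 75 | any look |
|---|---|---|---|
| 93.3% | 24.2% | 6.8% | 33.9% |
| 95% | 10.4% | 2.7% | 13.7% |
| 96.4% | 3.4% | 0.7% | 4.1% |

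Taking the earlier study's rates only as a scenario (93.3%, 97.1%, 96.8%) and treating arms as independent, the chance that at least one of three closes is 1 − (1 − 0.339)(1 − 0.017)(1 − 0.026) = 36.7%.

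**3. Size of the bias on crude ACPR.** The protocol gives no figure for change in re-infection over time, so the shift is an assumption. Take no dose effect, PCR-adjusted ACPR of 95% in every arm, and re-infection falling from 40% to 20% after the 75th child per arm. Treating re-infection as independent of cure:

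- early crude ACPR = 0.95 × 0.60 = 57%
- late crude ACPR = 0.95 × 0.80 = 76%
- an arm closed at 50 or 75 shows 57%
- an arm that runs to 150 shows (75 × 57% + 75 × 76%) / 150 = 66.5%

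The closed arm looks 9.5 points worse for reasons unrelated to dose. Rejection by a nominal 5% linear dose-trend test, given that the lowest-dose arm closes (simulation):

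| Re-infection shift | closed at 50 | closed at 75 | stratified by stage |
|---|---|---|---|
| none | about 5% | about 5% | about 5% |
| 35% to 25% | about 7% | 8-9% | about 5% |
| 40% to 20% | 11% (4 arms), 14% (3 arms) | 16% (4 arms), 20% (3 arms) | about 5% |

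A separate logistic simulation, with three arms and the shift placed at closure, agrees. With crude ACPR moving from 60% to 75% after a closure at 50, the closed arm shows 60% against (50 × 60% + 100 × 75%) / 150 = 70%. The false odds ratio is about 1.19 per 300 mg, with rejection in 15% of trials and about 5% once a period term is added.

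**4. Size of the bias on PCR-adjusted ACPR.** In the same logistic simulation, assumed shifts of 95% to 97% and 93% to 97% give rejection of about 6% and 8-9%. With a period term the figure is 3-5%.

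**5. Not conditioning on a closure.** Apply the actual futility rule to four arms, all at 95%, where any arm may close or none. The crude trend test then rejects in about 10% of trials for the 40% to 20% shift and about 7% for 35% to 25%.

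**The case against.** Several objections have force.

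- **Left to the SAP.** Section 11 is declared the basis of the SAP, which is not at hand, and nothing in the protocol forbids a period term. That is true. But the protocol itself sets up the arm-by-arm closure and already names the model, the population and the outputs. A rule that follows directly from the adaptation belongs beside it, fixed before any arm closes.
- **The trend is assumed.** The protocol gives no seasonality. The 22.6 to 43.3 point gaps between adjusted and uncorrected cure in Section 4.2.2 are differences across doses, not over time. This stands: without a trend there is no inflation.
- **The headline is conditional.** The 33.9% closure rate supposes a true lowest-dose rate of 93.3%. The 10-20% supposes no dose effect and a closure that has happened. The two must not be joined. Under equal rates every arm is equally likely to close. Skipped looks, or enrolment that continues while Day 28 data are awaited, would also shrink the non-concurrent group.
- **Status of the analyses.** They are secondary or exploratory. The curves carry no between-arm test, and p-values are promised only for PCR-adjusted ACPR, where the inflation is modest. For crude ACPR the trend test used here is an illustration of the bias, not a stated analysis.

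A reader might also infer that the age step-down makes early and late children differ by design. The documents support this only weakly. Section 7.4.2 asks for a minimum of 8 children per arm in each of Cohorts 3 and 4, which at those minimums is complete before the first look at 50. Randomisation is stratified by age class, and per-cohort analyses are planned.

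**Conclusion.** The point holds in conditional form. If an arm is closed for futility and transmission changes during enrolment, the all-patient dose-response analyses and by-arm recurrence curves can be confounded by enrolment period. Closure is a realistic event, from 4.1% to 33.9% per arm over the true rates considered. The bias could be material for crude ACPR and re-infection and is modest for PCR-adjusted ACPR; its size rests wholly on the assumed shifts.

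Two stronger readings are not supported. False dose effects do not follow automatically, because both a closure and a time trend are needed. The primary conclusion is not at risk, because each arm is tested against a fixed 0.90 and no arms are compared. The change is worth making because it removes the problem at almost no cost and the results are meant to inform the Phase III dose.

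**What to change.** Add to Sections 11.4.3.2 and 11.4.5.3.1 that, if any arm is closed early:

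- the dose-response models for PCR-adjusted and PCR-crude ACPR include a stratum or fixed term for enrolment stage, defined as the intervals between arm closures and taken from the randomisation date;
- between-arm Kaplan-Meier displays of re-emergence, recrudescence and re-infection are stratified in the same way, or restricted to patients randomised while all the compared arms were open.

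The primary test, sample size and data collection do not change. The one small cost is that patients randomised after a closure inform only comparisons among the arms still open.
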